5.5.6. Rescue Therapy

Rescue therapies include rescue medications and rescue procedures including surgeries. The number of participants receiving rescue therapies (medication or procedures) between 3 and 12 hours post-randomization, as well as the total number of therapies received, will be summarized based on dose of andexanet received (low, high, and total) or the type of UC initially received (PCC, other, no treatment, and total). The CMH test stratified by time from symptom onset to the baseline imaging scan will be used to test the treatment difference in the proportion of participants receiving at least 1 rescue therapy between andexanet and UC. The p-value and 95% CI of the difference in proportion will be presented.

The types of rescue medications used will be tabulated by treatment group; participants reporting > 1 medication within an Anatomical Therapeutic Chemical (ATC) classification or a generic name will be counted only once for that class or name. In addition, the surgeries/procedures used to treat the index hematoma or could impact hematoma volume will be tabulated by treatment group; participants reporting > 1 surgery/procedure will be counted only once for that surgery/procedure.

A by-participant listing of rescue therapies will be provided.

5.5.7. Correlation Between Anti-fXa Activity and Effective Hemostasis

The correlation between the achievement of effective hemostasis and the percent change from baseline to nadir in anti-fXa activity 2 hours post-randomization will be evaluated. Missing data of anti-fXa activity will be imputed using the multiple imputation method described in Section 5.4. Nonevaluable effective hemostasis status will be treated as poor/none regardless of reason. A logistic regression will be used for the analysis, where the dependent variable is effective hemostasis status, the independent variable is the treatment group, and covariates include time from symptom onset to the baseline imaging scan, percent change from baseline to nadir in anti-fXa activity, and baseline anti-fXa activity. From this model, the odds ratio for the treatment effect, the area under the curve (AUC) with varying threshold for percent change from baseline to nadir in anti-fXa activity, and the 95% CI will be estimated. The same analysis will also be performed for change from baseline to nadir in anti-fXa.

5.5.8. European Quality of Life 5-Dimension 5-Level

Health-related quality of life assessed by the European Quality of Life 5-Dimension (EQ-5D) questionnaire at 30 days post-randomization is collected either on the participant or through a medical proxy. For analyses, data for both participant and proxy will be pooled. The pooled data will be summarized by treatment group by European Quality of Life 5-Dimension 5-Level (EQ-5D-5L). Comparison between andexanet and UC will be performed for each dimension in terms of "no problems" (Level 1) and "any problems" (Levels 2, 3, 4, and 5), using a CMH test adjusting time from symptom onset to the baseline imaging scan.

Statistical Analysis Plan ALXN2070 18-513 (Amendment 3)

The EQ-5D-5L index value and visual analog scale will be summarized as continuous variables. The difference between treatment groups will be evaluated using an ANCOVA adjusted for time from symptom onset to baseline imaging scan. The LS mean difference between the 2 treatment groups and its 95% CI will be presented.

By-participant listings of EQ-5D-5L data will be provided.

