1.0 INTRODUCTION

The class of Novel Oral Anticoagulants known as direct Factor Xa (FXa) inhibitors has consistently demonstrated comparable or superior efficacy and/or safety relative to its predecessors, Vitamin K Antagonists (VKAs) and Low Molecular Weight Heparins. These agents (apixaban [Eliquis[®]], betrixaban [BevyxXa[®]], edoxaban [Savaysa[®]], rivaroxaban [Xarelto[®]]) are approved for the prevention of serious thromboembolic outcomes (e.g., stroke, deep vein thrombosis [DVT], pulmonary embolism [PE]) and have become widely used in the United States (US) and worldwide. One limitation to the use of FXa inhibitors has been the lack of an antidote to be used in cases of severe and/or life-threatening bleeding events. Acute major bleeding occurs at observed rates of 2-4% in pivotal stroke prevention trials in patients with nonvalvular atrial fibrillation [1-3], and such events are often catastrophic. Given the wide adoption and increasing use of FXa inhibitors, the prospect of major bleeding, especially in Intracranial Hemorrhage (ICrH) patients, has become a significant unmet medical need.

Among the various types of bleeding, the most serious and consequential is ICrH, including intracerebral/intraventricular, subdural, subarachnoid, and epidural bleeding. Patients with ICrH have particularly dismal outcomes, with 30-day mortality rates in excess of 30-40% [1-3] and a 75% 1-year incidence of severe disability or death [4]. In the management of patients with ICrH, a primary therapeutic goal is the prevention of hematoma expansion, which has been strongly associated with morbidity and mortality [5]. While investigation of the impact of hematoma expansion is limited by a lack of a unifying definition [6], a general consensus has arisen in recent years that a relative volume increase of 30-35% or less compared to baseline is indicative of a lack of expansion [7-9].

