5.5. Additional Endpoint Analysis

The tertiary efficacy endpoints are listed in Section 1.1. All tertiary efficacy analyses will be performed on the ITT Set. No missing data will be imputed.

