6.3.2. Utility-Weighted mRS

The determination of utility weights for the mRS will be determined as follows:

- mRS utilities represent preferences for mRS health states and range from < 1 to 1 (perfect health), where 0 indicates death.
- Utility values for each mRS health data will be elicited using the EQ-5D-5L responses of participant or proxy assessed at 30 days post-randomization (Chaisinanunkul, 2015). The EQ-5D-5L consists of 5 dimensions (mobility, self-care, usual activities, pain/discomfort, and anxiety/depression) with 5 levels each (no

problems, slight problems, moderate problems, severe problems, and unable to/extreme problems), thus defining 3125 distinct health states.

- Converting the EQ-5D-5L responses into EQ-5D utility values was done according to Table 7 below. Participants who died before the follow-up interviews at 30 days will receive a utility value of 0. The utility values range from < 0 (where 0 is the value of a health state equivalent to dead, and negative values represent values as worse than dead) to 1 (full health).
- The utility weights for each mRS category (1 to 5, excluding 6 which is death) will be determined by averaging the derived EQ-5D utilities of all participants within each of the mRS health states (eg, the utility weight for mRS = 1 is the average of the utilities of all participants with mRS = 1).
- The utility weights as derived above will be used in analyses.

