6.3.3. EQ-5D-5L Health State Index Score Calculations

The responses to the 5 EQ-5D dimensions can be converted into a single number called an index value. The EQ-5D-5L health state index score is derived by applying a formula that attaches values (also called weights) to each of the levels in each dimension. The index can be calculated by subtracting the appropriate weights for each dimension level of health state from 1. The EQ-5D-5L index scores for this study will be obtained using the US composite time trade-off method (Pickard, 2019; Mehta, 2011). The calculation is illustrated in below (Pickard, 2019):

US cTTO		Example: The value for health state is 21354
Full health (11111)		Full health $= 1$
Mobility Level 2	-0.096	-0.096
Mobility Level 3	-0.122	
Mobility Level 4	-0.237	
Mobility Level 5	-0.322	
Self-care Level 2	-0.089	0
Self-care Level 3	-0.107	
Self-care Level 4	-0.220	
Self-care Level 5	-0.261	
Usual activity Level 2	-0.068	
Usual activity Level 3	-0.101	-0.101

Table 7:EQ-5D-5L US cTTO Value Set

US cTTO		Example: The value for health state is 21354
Usual activity Level 4	-0.255	
Usual activity Level 5	-0.255	
Pain/discomfort Level 2	-0.06	
Pain/discomfort Level 3	-0.098	
Pain/discomfort Level 4	-0.318	
Pain/discomfort Level 5	-0.414	-0.414
Anxiety/depression Level 2	-0.057	
Anxiety/depression Level 3	-0.123	
Anxiety/depression Level 4	-0.299	-0.299
Anxiety/depression Level 5	-0.321	
Health state index score		=1 - 0.096 + 0 - 0.101 - 0.414 - 0.299 = 0.090

Table 7:EQ-5D-5L US cTTO Value Set

Abbreviation: cTTO = composite time trade-off; EQ-5D-5L = European Quality of Life 5-Dimension 5-Level; US = United States

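### As written, the Day-30 EQ-5D-5L index is compared among questionnaire respondents only: participants who died get no index, although SAP 6.3.2 values death at 0 on the same scale

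*SAP*

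**What the plan says.** The quality-of-life objective has two endpoints, both at 30 days: EQ-5D and the utility-weighted mRS (Table 1 of each document). The relevant provisions are spread over five SAP sections.

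- **SAP 5.5.8 (EQ-5D-5L).** The "questionnaire at 30 days post-randomization is collected either on the participant or through a medical proxy". "The EQ-5D-5L index value and visual analog scale will be summarized as continuous variables". For both of these, "The difference between treatment groups will be evaluated using an ANCOVA adjusted for time from symptom onset to baseline imaging scan", with an LS mean difference and 95% CI. Deaths are not mentioned. Protocol 9.1.6 also allows the form at an Early Termination visit.
- **SAP 5.5 (additional endpoints).** "All tertiary efficacy analyses will be performed on the ITT Set. No missing data will be imputed".
- **SAP 6.3.3 (index derivation).** "The index can be calculated by subtracting the appropriate weights for each dimension level of health state from 1". The calculation needs an answer on each of the five dimensions, and no value is given for death.
- **SAP 6.3.2 (utility-weighted mRS).** "Participants who died before the follow-up interviews at 30 days will receive a utility value of 0". The sentence stands in the item on converting EQ-5D-5L responses with Table 7, which is also the value set used in 6.3.3.
- **SAP 5.5.9 (utility-weighted mRS results).** Mean and SD of the utilities for each mRS score by arm, with no difference between arms.

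Neither 5.5.8 nor 6.3.3 refers to the death rule in 6.3.2.

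**The concern.** Responding to a Day-30 questionnaire requires being alive, and survival is an outcome that treatment may change. The protocol gives reasons for an effect in either direction: section 1.0 links hematoma expansion to mortality, and section 3.5 says that reversing anticoagulation raises thrombotic risk. If mortality differs between arms, the respondents in the two arms are no longer comparable groups, even though the analysis is labelled ITT.

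Suppose andexanet keeps alive patients who are then severely disabled. They enter its mean with low values, while their counterparts on usual care are absent, so the drug appears to lower quality of life. If andexanet instead caused deaths among such patients, its respondent mean would rise.

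The comparisons in 5.5.8 are the only between-arm comparisons that the SAP spells out under the quality-of-life objective, so no specified utility contrast counts deaths. In addition, two analysts could treat the 6.3.2 rule differently for the index and report differences of opposite sign from the same data.

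**Working it through.** **Step 1. The plan's own figure.** For health state 21354, SAP Table 7 gives 1 - 0.096 - 0 - 0.101 - 0.414 - 0.299 = 0.090, as stated. The worst state gives 1 - 0.322 - 0.261 - 0.255 - 0.414 - 0.321 = -0.573. The index therefore runs from -0.573 to 1, and 6.3.2 places death at 0 within that range. Death has a defined value on the scale, but the questionnaire cannot supply it.

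**Step 2. Formulas.** Let s be survival on usual care, d the additional survival on andexanet, m the mean index of patients who survive under either treatment, and u the mean index of the additional survivors. Assume that every survivor responds and that treatment does not change the index of patients who would survive anyway.

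- Respondents only: (s·m + d·u)/(s + d) - m = d(u - m)/(s + d)
- Deaths at 0, all randomized: (s·m + d·u) - s·m = d·u

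The first is negative when u < m and the second is positive when u > 0. With d > 0, the respondents-only difference is negative while the other is positive exactly when 0 < u < m.

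**Step 3. Numbers.** All inputs are assumptions except u = 0.09, which borrows the SAP's example state. Usual-care mortality is 35% (s = 0.65), d = 0.05 and m = 0.50.

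| u | Andexanet respondent mean | Respondents only | Deaths at 0 |
|---|---|---|---|
| 0.10 | 0.330/0.70 = 0.471 | -0.029 | 0.330 - 0.325 = +0.005 |
| 0.09 | 0.3295/0.70 = 0.471 | -0.029 | +0.0045 |
| 0.20 | 0.335/0.70 = 0.479 | -0.021 | +0.010 |
| 0.70 | 0.360/0.70 = 0.514 | +0.014 | +0.035 |
| -0.20 | 0.315/0.70 = 0.450 | -0.050 | -0.010 |

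The signs differ in the first three rows and agree in the last two.

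**Step 4. Range.** Keep u = 0.09 and vary usual-care mortality over 30-40%, d over 0.03-0.08 and m over 0.4-0.6. The respondents-only difference runs from 0.03 × (-0.31)/0.73 = -0.013 to 0.08 × (-0.51)/0.68 = -0.060. With deaths at 0 it runs from 0.03 × 0.09 = +0.003 to 0.08 × 0.09 = +0.007.

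**Step 5. Lower mortality, and harm instead of benefit.** At 20% versus 15% mortality with m = 0.50 and u = 0.10, the differences are 0.05 × (-0.40)/0.85 = -0.024 and +0.005. If andexanet mortality were 40% against 35%, with the extra deaths among patients who would have scored 0.10, the usual-care respondent mean is (0.60 × 0.50 + 0.05 × 0.10)/0.65 = 0.469 against 0.500. Respondents only then shows +0.031, while deaths at 0 shows 0.300 - 0.305 = -0.005.

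**Step 6. Precision.** With 0.70 × 450 = 315 and 0.65 × 450 = 292.5 expected respondents and an assumed SD of 0.25-0.35, the standard error is SD × √(1/315 + 1/292.5), or 0.020-0.028. The -0.029 is therefore about 1.0 to 1.4 standard errors.

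**The case against.** The strongest reply is that no sentence excludes deaths. The analyses are on the ITT Set, and the rule in 6.3.2 is written for individual participants' EQ-5D utilities from the same Table 7, so an analyst could carry it over to the index. This stands in part: a reader might infer that the SAP prescribes a survivors-only analysis, but the exclusion only follows from reading 5.5, 5.5.8 and 6.3.3 together. The set is also respondents rather than survivors, because Early Termination forms are accepted and survivors without a form drop out too. The reply does not remove the problem, since following 5.5.8 literally still leaves deaths without an index.

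A reader might also infer that the two quality-of-life endpoints treat the same patients in opposite ways. The documents do not support that. SAP 5.5.9 has no between-arm contrast to conflict with, and both the Protocol Synopsis and the end of 6.3.2 point to some further utility-weighted analysis that they do not specify.

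Nor do the documents show that about a third of each arm will be lost. Protocol 1.0 cites "30-day mortality rates in excess of 30-40" percent as background for intracranial hemorrhage generally. This trial excludes GCS below 7, NIHSS above 35, volumes above 60 mL, and expected survival under one month for reasons unrelated to the bleed.

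Deaths are visible elsewhere. The dichotomised mRS counts them as unfavourable (SAP 5.5.3), and mortality has its own Cox and Kaplan-Meier analyses (SAP 5.7.2.5). That limits how far a reader could be misled, but it does not repair the index comparison. Finally, valuing death at 0 is one choice of estimand, and it mixes mortality with quality of life. That is fair, but the SAP has already adopted that value on this scale.

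**Conclusion.** The point holds as a gap with a definite consequence. Read literally, the plan compares the EQ-5D-5L index among respondents, and that is not a randomized comparison if treatment affects mortality. In the illustration the difference is -0.029 among respondents against +0.005 with deaths at 0.

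The size rests on assumed mortality, mortality difference and utilities; the documents give none of these for the trial. The sign reversal is conditional. It occurs when the additional survivors' mean index lies between 0 and the survivor mean, and not when they score above that mean or below 0. The inference that the planned analysis will show a false harm therefore goes too far; it can do so. In the worked case the respondents-only difference would also be within about 1.4 standard errors.

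EQ-5D is an additional endpoint outside the hierarchical testing in SAP 5.1.1, so the primary and secondary conclusions are unaffected.

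**What to change.** In SAP 5.5.8, make the main index comparison on the ITT Set with the index set to 0 for participants who died by Day 30, by reference to 6.3.2. Keep the respondents-only index as a supportive analysis. Leave the VAS and per-dimension comparisons as planned, since the SAP gives no death value for either, but label them as conditional on response. Show the numbers of deaths and of living non-respondents by arm beside them.

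The cost is a sentence or two in the SAP, and no new data are needed because deaths are already recorded and adjudicated. There are two downsides: the index distribution gains a spike at 0, and the index then combines mortality with quality of life. The change removes selection by death. Survivors without a form remain missing under SAP 5.5, which is why their number should be reported.

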5.5.9. Utility-Weighted mRS

Details on calculation of utility weights are specified in Section 6.3.2. The mean and SD of the utility values will be presented for each mRS score by treatment group.

5.6. Additional Analysis

Values at each visit and change and percent change from baseline in tissue factor pathway inhibitor (TFPI) data at baseline (most recent measurement within 15 minutes prior to randomization), at 1, 2, and 12 hours, and at Day 30 post-randomization will be summarized using descriptive statistics.

By-participant listings of TFPI data will be provided.

5.7. Safety Analyses

Safety endpoints are listed in Section 1.1. Generally, all safety analyses will be based on the Safety Set. If the study is stopped after interim analysis, safety analyses will be based on the final data cutoff unless otherwise specified.

5.7.1. Extent of Exposure

Participant compliance with the assigned treatment will not be evaluated as all procedures are performed in the hospital by a trained professional.

For the participant who received and examet, summaries will be presented by the dose of and examet received (low, high, and total). The number and percentage of participants with any treatment modification (dose not changed, study drug interrupted, study drug withdrawn, dose reduced, dose increased, not applicable, and unknown), along with descriptive statistics on the length of bolus and infusion duration, will be summarized.

For participants who received UC, the following data will be tabulated by the type of UC initially received (PCC, other, no treatment, and total):

- Whether PCC was used to acutely manage the participant
- The initial number of therapies received
- The therapy received

By-participant listings of andexanet and UC administration will be provided.

5.7.2. Adverse Events

AEs are defined in Protocol Section 8. An AE is any untoward medical occurrence in a clinical investigation participant administered a pharmaceutical product, regardless of causal attribution

Page 26 of 52 Alexion Confidential to study treatment or procedure. A treatment-emergent adverse event (TEAE) is any AE that occurs at any time following treatment initiation.

The number of events and the number and percentage of participants who experienced at least 1 TEAE reported through the Day 30 Follow-up Visit will be presented. TEAEs that are considered by the Investigator to be related to either the study intervention or the UC, TEAEs that lead to early withdrawals of study drug, and serious adverse events (SAEs) will be summarized in the same manner.

All SAEs and TEAEs leading to study intervention withdrawal or interruption will be listed separately.

5.7.2.1. Overall Summary of AEs

An overall summary of AEs and SAEs will be presented. The number of AEs and the number of participants with AEs (n, %) will be shown by treatment group and total (Table 4).

Events
Any TEAE
Any TESAE
Any related TESAE
Deaths
TEAEs leading to withdrawal or interruption of study intervention
TESAEs leading to withdrawal or interruption of study intervention
TEAEs by relationship (related and not related)
TEAEs by severity (mild, moderate, and severe) ^a
TESAEs by relationship (related and not related)
AESIs (thrombotic events: arterial systemic embolism, deep vein thrombosis, myocardial infarction, pulmonary embolism, stroke, and transient ischemic attack)

Table 4:AEs and SAEs

^a Severe includes life-threatening and fatal events.

Abbreviations: AE=adverse event; AESI=adverse event of special interest; SAE=serious adverse event

5.7.2.2. AEs and SAEs by SOC and PT

The number of TEAEs and the number and percentage of participants with events will be presented by System Organ Class (SOC) and Preferred Term (PT). Participants are counted once in each SOC and PT. Percentages will be based on the total number of treated participants in each treatment group and total (andexanet plus UC). SOCs will be listed in alphabetical order, and PTs within each SOC will be sorted by descending frequency of participants, reporting the TEAEs in the total column.

TESAEs, TEAEs leading to interruption and withdrawal of study drug, frequent TEAEs including PTs with an incidence rate of \geq 5%, and adjudicated TEs leading to death will be tabulated in a similar manner.

Page 27 of 52 Alexion Confidential

5.7.2.3. AEs and SAEs by SOC, PT, and Relationship

The number and percentage of participants with events will be presented by SOC and PT, as described above, by the highest relationship (related or not related). If a participant has > 1 occurrence of a TEAE with different relationship status, the related occurrence will be summarized for each participant per SOC/PT. In addition, the number of TEAEs and the number and percentage of participants with TEAEs will be presented by SOC and PT for all relationship levels (related and not related); if a participant has multiple events at the same relationship status for a particular SOC or PT, he/she is counted only once for that SOC or PT, but all occurrences are counted at the event level. SAEs will be summarized similarly.

Treatment-related TEAEs will also be tabulated, at the PT level only, for the number and percentage of participants, as well as for the number of events, with PTs sorted by descending frequency of participants, reporting the PTs in the total column.

5.7.2.4. AEs and SAEs by SOC, PT, and Severity

The number and percentage of participants with events will be presented by SOC and PT, as described above, by worst severity (mild, moderate, or severe). If a participant has > 1 occurrence of a TEAE, the most severe occurrence will be summarized for each participant per SOC/PT. In addition, the number of TEAEs and the number and percentage of participants with events will be presented by SOC and PT for all severity levels. If a participant has multiple events at the same severity for a particular SOC or PT, he/she is counted only once for that SOC or PT, but all occurrences are counted at the event level.

5.7.2.5. Deaths

The number and percentage of participants with AEs leading to death will be presented by SOC and PT as described above.

All deaths will be assessed by the EAC blinded to treatment group. Deaths occurring up to 30 days post-randomization will be referred below as 30-day death or 30-day mortality. Bleeding mortality is defined as deaths occurring within 72 hours post-randomization not associated with TEs.

All 30-day deaths, 30-day death occurring during index hospitalization, and bleeding-related mortality (defined as any death within 72 hours from randomization and not associated to the occurrence of an identified TE) will be summarized by treatment group and total based on the following causes:

- All causes
- Cardiovascular (CV) causes (resulting from myocardial infarction, sudden cardiac death, heart failure, stroke, cerebral vascular procedures, CV hemorrhage, or other)
- Non-CV causes (resulting from non-CV hemorrhage and non-CV procedure or surgery)

Time to death by all causes up to 30 days post-randomization will be analyzed using a Cox proportional hazards model adjusted for time from symptom onset to the baseline imaging scan (< 180 minutes versus \geq 180 minutes) and treatment group. Participants who did not die or discontinued prior to Day 30 will be censored at the day of the last assessment.

Page 28 of 52 Alexion Confidential Kaplan-Meier method will be used to analyze time to death with the same censoring rule. Participants who completed the study (ie, Day 30) will be censored at the day of the last assessment. Probabilities of 30-day death at different time points and median time to death will be presented by treatment group.

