3.4. Safety Plan and Monitoring

The study will be conducted in patients who, by virtue of their condition, will typically be in acute care settings such as intensive care units and EDs. It is anticipated that patients with acute intracranial bleeding will remain hospitalized for well over 12 hours, the timeframe for the primary efficacy evaluations. During the first 24 hours after randomization (Study Day 1), AEs, vital signs, clinical neurologic testing, and brain imaging will be performed to monitor safety. If a patient has a clinically significant, new or worsening, focal or global neurologic deficit relative to baseline (e.g., an increase from baseline in the NIHSS score of 5 or greater), that is not readily explainable by an alternate etiology (e.g., sedatives, infection), Investigators will be requested to

pursue additional brain imaging. Investigators will also be allowed to scan patients for any medically indicated reason at their discretion.

After Study Day 1, all patients will be followed for AEs (including TEs) through the Day 30 visit. Survival status will be documented through Day 30, and the cause and date/time of death will be recorded, if applicable. Finally, patients will be assessed for antibodies to FX, FXa, and andexanet at the Day 30 visit. If a patient has a positive anti-andexanet antibody response at the Day 30 visit, they will return for a follow up anti-andexanet antibody test approximately 120 days after randomization, or within 30 days of when the positive test is made known to the Investigator, whichever is later.

Whether or not patients remain in the hospital, they will undergo the Study Day 2, Day 3, Day 7 (phone call), Day 14 (phone call), and Day 30, and Day 120 (as applicable) Follow-up visits to assess outcomes.

The independent EAC, in addition to adjudicating the primary efficacy endpoint, will also adjudicate all potential TEs using pre-defined criteria as described in the Adjudication Charter, as well as AESI and deaths. In addition, the independent DSMB will be empowered to recommend modifying or stopping the trial for safety reasons if warranted.

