4.3. Criteria for Discontinuation from the Study

A patient may elect to discontinue participation in the study at any time. However, all efforts must be made to follow patients for the full duration of the study and to encourage all patients to complete the Day 30, and Day 120 (as applicable) contact.

If patients cannot or will not return for visits, the Investigator (or their designee) should attempt to contact them by telephone or other means; those who cannot be contacted should be considered lost to follow-up.

Reasons for all study withdrawals will be recorded. If a patient withdraws from the study, the patient may request destruction of any samples taken and not tested, and the Investigator must document this request in the site study records.

Patients who discontinue study procedures for reasons other than withdrawal of consent can still have Day 30 mortality status collected.

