4.6. Study Completion

Study completion for each patient is defined as completion of the Day 30 visit or, at a minimum, the time at which Day 30 mortality status is recorded. For patients with a positive anti-andexanet antibody response at the Day 30 visit, study completion is defined as completion of the follow-up visit approximately 120 days post-randomization, or within 30 days of when the positive test is made known to the Investigator, whichever is later.

All events and analyses occurring by Day 30 will be described in a primary clinical study report. Additional events and analyses for the period between Day 30 and Day 120 (if applicable) will be described in a safety follow-up clinical study report.

In some countries, "study completion" may also be considered the same as "end of trial."

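### Read literally, the SAP 5.7.2.5 censoring rule drops known deaths after study discontinuation from the Cox and Kaplan-Meier analyses of 30-day mortality, while the table of 30-day deaths keeps them

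*SAP*

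**What the plan says.** SAP 5.7.2.5 sets out three mortality outputs.

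- **Cox model.** "Time to death by all causes up to 30 days post-randomization will be analyzed using a Cox proportional hazards model", adjusted for treatment group and the onset-to-scan stratum. The censoring rule follows: "Participants who did not die or discontinued prior to Day 30 will be censored at the day of the last assessment".
- **Kaplan-Meier.** "Kaplan-Meier method will be used to analyze time to death with the same censoring rule". A further sentence there censors participants who completed the study at the day of their last assessment.
- **Descriptive table.** "All 30-day deaths, 30-day death occurring during index hospitalization, and bleeding-related mortality" are summarized by treatment group and cause. The section defines the term by time since randomization alone: "Deaths occurring up to 30 days post-randomization will be referred below as 30-day death or 30-day mortality".

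The protocol follows survival beyond the end of study procedures. Section 3.4 says "Survival status will be documented through Day 30, and the cause and date/time of death will be recorded, if applicable". Section 4.3 adds "Patients who discontinue study procedures for reasons other than withdrawal of consent can still have Day 30 mortality status collected". Section 4.6 defines completion as the Day 30 visit or "at a minimum, the time at which Day 30 mortality status is recorded". SAP 5.2.1, by contrast, ties completion to the 30-day follow-up visit.

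**The concern.** The censoring sentence has two limbs: participants who did not die, and participants who discontinued before Day 30. Every survivor already falls under the first. The second therefore changes the result only for someone who discontinued and then died, and it turns that death into a censored observation at an earlier date.

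Two things are at stake. First, the Cox model is the only modelled between-arm comparison among the safety analyses in SAP 5.7, so events missing from it are missing where the arms are formally compared. Second, the same section counts those deaths in its table, so a report could show one number of 30-day deaths in the table and a smaller number of events in the model, with no rule to reconcile them.

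A related gap concerns survivors. The SAP does not define the last assessment or say whether a vital-status contact counts as one, so the censoring date of a discontinued participant known to be alive at Day 30 is not fixed.

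**Working it through.** **Reading the rule.** Take four participants who stop study procedures on Day 5 and do not come back for visits.

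| Known status | Table of 30-day deaths | Cox / Kaplan-Meier, literal rule |
|---|---|---|
| Died Day 20, recorded | Counted | Censored about Day 5 |
| Alive at Day 30 by vital-status contact, contact not treated as an assessment | Not a death | Censored about Day 5 |
| Alive at Day 30 by vital-status contact, contact treated as an assessment | Not a death | Censored about Day 30 |
| Consent withdrawn, nothing further known | Not a death | Censored about Day 5 (appropriate) |

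The first row is the defect. The second and third rows are the ambiguity. Protocol 4.6 makes that survivor a completer and SAP 5.2.1 does not.

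**Size.** The plan states no event count, hazard ratio or discontinuation rate for mortality, so there is no figure of its own to reproduce. Everything below is illustration.

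*Inputs from the documents:* 450 patients per group (protocol 10.3); 30-day mortality in excess of 30-40% in intracranial hemorrhage (protocol 1.0). *Assumed:* a fraction d stops at a time C uniform on Days 1-14, with vital status obtained afterwards.

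*Scenario A: 30% mortality, early deaths, stopping unrelated to prognosis.* Death times among those who die are exponential with mean 8 days, capped at Day 30. The share of deaths falling after C is d × E[exp(-C/8)], and

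E[exp(-C/8)] = 8 × (e^(-1/8) - e^(-14/8)) / 13 = 8 × (0.8825 - 0.1738) / 13 = 0.436.

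With 0.30 × 450 = 135 deaths per arm:

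| d | Share of deaths dropped | Per arm |
|---|---|---|
| 3% | 1.3% | 1.8 |
| 5% | 2.2% | 2.9 |
| 10% | 4.4% | 5.9 |

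A simulation of 20,000 patients gave 1.2%, 1.9% and 4.8%, or 1.6, 2.5 and 6.6 deaths per arm. Together these give about 1-5%, or roughly 2-7 deaths per arm. With 1,000,000 simulated patients, Kaplan-Meier mortality under the literal rule was 30.0/29.9/30.0% against a true 30.0/29.9/30.0%. Events are lost, but the estimate is not biased.

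*Scenario B: the hazard doubles after stopping.* Use a constant hazard λ = -ln(1 - m)/30 before stopping, where m is 30-day mortality without the increase. Kaplan-Meier with discontinuers censored recovers m. True mortality exceeds m by d × (q2 - q1), where

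- q1 = E[e^(-λC)] - (1 - m) is the chance of being alive at C and dying by Day 30 with the hazard unchanged;
- q2 = E[e^(-λC)] - (1 - m)² × E[e^(λC)] is the same with the hazard doubled.

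For m = 0.30: λ = 0.01189, q1 = 0.9156 - 0.7000 = 0.2156, q2 = 0.9156 - 0.49 × 1.0944 = 0.3794, difference 0.1638. For m = 0.40: λ = 0.01703, q1 = 0.8819 - 0.6000 = 0.2819, q2 = 0.8819 - 0.36 × 1.1385 = 0.4720, difference 0.1901.

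| d | Deaths dropped per 900 (900 × d × q2), m = 30% / 40% | Understatement in points, m = 30% / 40% |
|---|---|---|
| 2% | 6.8 / 8.5 | 0.33 / 0.38 |
| 5% | 17.1 / 21.2 | 0.82 / 0.95 |
| 10% | 34.1 / 42.5 | 1.64 / 1.90 |

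The range is about 0.3-1.9 points. A simulation of the same model agrees to within 0.04 points.

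**The case against.** The best defence is that the section defines 30-day death by time since randomization before it introduces the model, so a sensible programmer would treat every known death as an event and apply the censoring sentence only to people without one. That is probably the intent. It is not what the sentence says, and on that reading the discontinuation limb would do nothing. A rule whose plain wording has to be overridden should be corrected.

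Several other objections stand, and they rule out stronger readings that a reader might infer.

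- *That Day 30 vital status is discarded altogether.* It is not. The table of all 30-day deaths has no on-study condition, so the loss is confined to Cox and Kaplan-Meier.
- *That the status of every discontinued patient is in the database.* Protocol 4.3 is permissive and leaves out withdrawal of consent, and some patients will be lost to follow-up. The affected group is those who stopped procedures, did not withdraw consent and had their status obtained.
- *That Kaplan-Meier mortality is overstated because deaths are kept while known survivors leave early.* Under Scenario A inputs that would be about 0.3-1.2 points, but it requires survivors to be censored at the last visit. Under protocol 4.6 they are completers and could be censored at about Day 30. The documents do not settle this.
- *That the comparison between arms is biased.* The trial is open-label and stopping could differ by arm, but nothing in the documents shows that it would. No between-arm bias has been calculated, and its direction cannot be stated in advance.

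The analysis also lies outside the tested primary and secondary hierarchy, so no error rate or power figure is affected.

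**Conclusion.** The concern holds for the two time-to-event analyses. As written, the rule censors known deaths after discontinuation, contrary to the SAP's own definition of 30-day death and to the survival follow-up in protocol 3.4, 4.3 and 4.6. It also leaves the censoring date of known survivors open.

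The expected effect is modest and rests on an assumed discontinuation rate. A few percent of deaths would be dropped, with no Kaplan-Meier bias if stopping carries no prognostic information. Mortality would be understated by up to about 2 points if one in ten stops and the hazard then doubles. The correction should be made before unblinding because the rule gives a wrong result for identifiable patients and is easy to put right.

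**What to change.** Replace the censoring sentences in SAP 5.7.2.5, for both Cox and Kaplan-Meier, with rules to this effect:

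1. Every death known to have occurred within 30 days of randomization is an event on its date, whether or not the participant discontinued.
2. Participants known from any source, including a vital-status contact, to be alive at or after Day 30 are censored at Day 30.
3. All others, including those who withdrew consent or were lost to follow-up, are censored at the last date known alive.
4. The number per arm with unknown Day 30 status is reported beside the estimates.

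Rule 2 makes the censoring date independent of which completion definition applies, though SAP 5.2.1 and protocol 4.6 should still be aligned. The cost is a few sentences and a small programming change. No new data are needed, since the rules use vital status only where it has been obtained.
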